#### Visit 4 a, b, c

- Visit 4a is a mandatory clinic visit. Visits 4b and Visit 4c may be a phone contact with the patient if (in discretion of the investigator) no clinically relevant abnormalities in ECG and vital signs are observed at visit 4a. Study procedures have to be completed according to the [Flow Chart](#).
- ECG and vital signs are only to be performed at clinic visits.

Proprietary confidential information.

© 2017 Boehringer Ingelheim International GmbH or one or more of its affiliated companies. All rights reserved.

This document may not - in full or in part - be passed on, reproduced, published or otherwise used without prior written permission.

- The attendance of the study partner is not necessarily required during the visits 4a-c.
- Patients should be advised to take the trial medication as per the drug label till the next scheduled visit. The importance of compliance to the study drug intake should be emphasized
- Administration of C-SSRS (since last visit scale).
- Patients should be reminded to return all used and un-used medication including the medication packaging back to the clinic at visit 5.
- Patient should be reminded to NOT take any study medication on the morning of visit 5.
- Patients are allowed to have a light breakfast/ meal before coming to the study site.
- Patients should be reminded not to take occasionally used sleeping aids (see [section 4.2.2.1](#)) in the evening prior to visit 5.
- Patient should be reminded to inform the study site in case of adverse events.

### Visit 5

- It is recommended to perform study procedures in the order as listed in the [Flow Chart](#).
- Study medication provided at visit 3 and returned should be collected and compliance check performed.
- Neuropsychological assessments should always be performed approximately at the same time (in the morning) in the order as stated in the [Flow Chart](#). Neuropsychological assessments and collection of urine and blood for laboratory testing must be performed prior to administration of study medication.
- For diabetic patients with antidiabetic therapy: exclusion of hypoglycemia for the period of the neuropsychological assessment (documented plasma glucose concentration  $\geq 90$  mg/dl (5mmol/l) at the beginning and directly after the assessment). If glucose is too low patients need to eat a snack and then be retested to confirm that the blood sugar value is above 90 mg/dl before the tests are started
- Administer the neuropsychological assessments in the following order:
  - CDR-SB
  - NTB
- Administration of C-SSRS (since last visit scale).
- New medication kits should be dispensed and the intake of trial medication and handling of medication blisters should be discussed with the patient and the study partner.
- The first dose of the study medication from the new kit should be taken under the supervision of the study staff.
- Patients should be advised to take the trial medication as per the drug label till visit 6. The importance of compliance to the study drug intake should be emphasized to the study partner as well.
- Patients should be reminded to get all used and un-used medication including the medication packaging back at visit 6.
- Patient should be reminded to NOT take any study medication on the morning of visit 6.
- Patients are allowed to have a light breakfast/ meal before coming to the study site.
- Patients should be reminded not to take occasionally used sleeping aids (see [section 4.2.2.1](#)) in the evening prior to visit 6.
- Patient should be reminded to inform the study site in case of adverse events.

Proprietary confidential information.

© 2017 Boehringer Ingelheim International GmbH or one or more of its affiliated companies. All rights reserved.

This document may not - in full or in part - be passed on, reproduced, published or otherwise used without prior written permission.

## Visits 6

- It is recommended to perform study procedures in the order as listed in the [Flow Chart](#).
- Study medication provided at visit 5 and returned should be collected and compliance check performed.
- Collection of urine and blood for safety laboratory testing
- C-SSRS (since last visit scale)
- New medication kits should be dispensed and the intake of trial medication and handling of medication blisters should be discussed with the patient and the study partner.
- [REDACTED]
- [REDACTED]
- The first dose of the study medication from the new kit should be taken under the supervision of the study staff.
- [REDACTED]
- Patients should be advised to take the trial medication as per the drug label till visit EOT. The importance of compliance to the study drug intake should be emphasized to the study partner as well.
- Patients should be reminded to return all used and un-used medication including the medication packaging back to the clinic at visit EOT.
- Patient should be reminded to NOT take any study medication on the morning of visit EOT.
- Patients are allowed to have a light breakfast/ meal before coming to the study site.
- Patients should be reminded not to take occasionally used sleeping aids (see [section 4.2.2.1](#)) in the evening prior to visit EOT.
- Patient should be reminded to inform the study site in case of adverse events.

## Visits 7 (End of Treatment/ Early Discontinuation visit)

- It is recommended to perform study procedures in the order as listed in the [Flow Chart](#).
- Study medication provided at visit 6 and returned should be collected and compliance check performed.
- Neuropsychological assessments should always be performed approximately at the same time (in the morning) in the order as stated in the [Flow Chart](#).
- For diabetic patients with antidiabetic therapy: exclusion of hypoglycemia for the period of the neuropsychological assessment (documented plasma glucose concentration  $\geq 90$  mg/dl (5mmol/l) at the beginning and directly after the assessment). If glucose is too low patients need to eat a snack and then be retested to confirm that the blood sugar value is above 90 mg/dl before the tests are started
- Administer the following neuropsychological assessments in the following order:
  - CDR-SB
  - NTB
  - ADCS-MCI-ADL
  - ADAS-cog11

Proprietary confidential information.

© 2017 Boehringer Ingelheim International GmbH or one or more of its affiliated companies. All rights reserved.

This document may not - in full or in part - be passed on, reproduced, published or otherwise used without prior written permission.

- C-SSRS (since last visit scale)
- Collection of urine and blood for safety laboratory testing.
- [REDACTED]
- [REDACTED]
- Visit EOT is the end of treatment visit. Study medication will not be taken at Visit EOT.

### **6.2.3 End of trial and follow-up period**

For all patients completing the study according to protocol, a follow-up contact (Visit FU) will be performed at the end of the follow-up phase of 28 days.

## 7. STATISTICAL METHODS AND DETERMINATION OF SAMPLE SIZE

### 7.1 STATISTICAL DESIGN - MODEL

This is a phase II multi-centre, double-blind, parallel-group, randomized, placebo-controlled study to investigate efficacy, safety and tolerability of orally administered BI 409306 once or twice daily during a 12-week treatment period compared to placebo in patients with prodromal Alzheimer's Disease. The primary endpoint is Neuropsychological Test Battery (NTB) response, defined as change from baseline in total z-score after 12-week treatment.

The primary analysis is the restricted maximum likelihood based mixed model repeated measurement (MMRM) comparing the change from baseline of NTB total z-score after 12-week treatment. Further analysis details are provided in [section 7.3](#) (Planned Analyses).

Another design aspect is the randomization allocation ratio of 1:1:1:1:2 of 10 mg, 25 mg, 50 mg, 25 mg BID of BI 409306 and placebo. Since the literature suggests that higher placebo response is related to the probability of patients receiving trial medication, the randomization allocation ratio is modified from a traditional equal ratio where only about 17 % of patients would receive placebo to an allocation ratio of 1:1:1:1:2 where 33 % of patients would receive placebo [[P10-10921](#)]. This is further elaborated in the [section 7.5](#) and the impact on sample size calculation is provided in [section 7.6](#).

### 7.2 NULL AND ALTERNATIVE HYPOTHESES

The objective of this exploratory trial is to demonstrate proof-of-concept and also explore the dose response of BI 409306 in NTB total score change from baseline (Visit 3) after 12 weeks treatment. The hypotheses testing will be carried in the following steps. No multiplicity adjustment will be made; hence all the p-values will be descriptive. All tests will be tested at a two-sided alpha 0.05.

- Step 1 for Proof-of-Concept:

$H_{1-0}$ : Mean NTB response of pooled doses of 10 mg QD, 25 mg QD, 25 mg BID and 50 mg QD = Mean NTB response of placebo

$H_{1-a}$  : Mean NTB response for pooled doses of 10 mg QD, 25 mg QD, 25 mg BID and 50 mg QD  $\neq$  Mean NTB response of placebo

If the null hypothesis  $H_{1-0}$  is rejected in favour of  $H_{1-a}$ , then the proof of concept is established.

- Step 2 for dose response finding:

A regression model will be fitted first as the following functional form.

$$\mu(d_i) = \beta_0 + \beta_1 d_i + \beta_2 d_i^2,$$

where  $\mu(d_i)$  denotes the mean response of NTB of the dose level  $i$  group,  $d_i$  denotes for dose levels  $i$ , for  $i = 1, 2, \dots, 5$  and  $\beta$ 's are the coefficients. The dose  $d_i$  will be treated as continuous variable.

Testing for linear dose response curve

$$H_{2-0}: \beta_1 = 0, \beta_2 = 0$$

$$H_{2-a}: \beta_1 \neq 0, \beta_2 = 0$$

If the null hypothesis  $H_{2-0}$  is rejected in favour of  $H_{2-a}$ , then the following test will be tested for quadratic dose response curve.

$$H_{3-0}: \beta_2 = 0$$

$$H_{3-a}: \beta_2 \neq 0$$

- Step 3:

Once the dose response curve is determined from Step 2, the dose group with peak response in the selected model will be tested as follows:

$H_{4-0}$ : The dose group with peak response in the respective model Mean NTB response = Mean NTB response of placebo.

$H_{4-a}$ : The dose group with peak response in the respective model Mean NTB response  $\neq$  Mean NTB response of placebo.

In addition to the 3 steps above, the confidence intervals of difference in treatment effect against placebo will be presented for efficacy evaluation.

Note Step 1 and Step 3 the testing will be based on the adjusted means of NTB response from the primary model as described in [section 7.3](#)

For the secondary endpoint, all calculated p-values should be considered as descriptive for the analysis of secondary endpoint. Therefore, no alpha correction will be carried out.

Proprietary confidential information.

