#### 4.1.3 Selection of doses in the trial

BI409306 has been tested in animal models to assess cognitive effects. On the basis of the described mode of action and the presented experimental efficacy in these animal memory tests, peak levels of BI 409306 in CSF in the range of 1x PDE9 IC50 need to be targeted for memory enhancing efficacy in humans. In a PoC study in healthy volunteers [[U12-2165-01](#)], it was shown that BI 409306 is able to cross the human blood-brain barrier (plasma to CSF) with a concentration corresponding to IC 50 (65 nmol/L) in CSF reached at 25 mg in 2 out of 4 subjects and exceeded IC 50 in all subjects at the higher doses. CSF exposure to BI 409306 increased with increasing dose and the CSF to plasma ratio for BI 409306 Cmax in humans is comparable to the one observed in rats and is constant over the entire dose range tested. CSF concentration-time profiles of BI 409306 peak approx. 0.5 to 1 hour later than in plasma and decline mono-exponentially and roughly in parallel to plasma concentrations afterwards with BI 409306 concentrations in CSF decreasing beyond the quantification limit (0.5 nmol/L) after 8 to 14 hours post dosing.

Therefore, the 25mg dose is anticipated to be the effective dose and will be tested once daily (QD) and twice daily (BID). To study the dose-response relationship, a lower dose (10mg) and a higher dose (50mg) will also be tested. For further details to the preclinical data as well to the human proof of mechanism study, please refer to the current version of the IB [[U11-1079](#)].

Patients will be randomized to one of five treatment groups as follows during the treatment period:

- BI 409306 10mg QD (Treatment Group 1)
- BI 409306 25mg QD (Treatment Group 2)
- BI 409306 50mg QD (Treatment Group 3)
- BI 409306 25mg BID (Treatment Group 4)
- Placebo (Treatment Group 5)

Proprietary confidential information.

© 2017 Boehringer Ingelheim International GmbH or one or more of its affiliated companies. All rights reserved.

This document may not - in full or in part - be passed on, reproduced, published or otherwise used without prior written permission.

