#### 7.6 DETERMINATION OF SAMPLE SIZE

The primary efficacy hypothesis will be tested by comparing the dose group of BI 409306 with the peak response in the fitted regression model to the placebo group on the primary

Proprietary confidential information.

© 2017 Boehringer Ingelheim International GmbH or one or more of its affiliated companies. All rights reserved.

This document may not - in full or in part - be passed on, reproduced, published or otherwise used without prior written permission.

endpoint, the change from baseline in NTB total score after 12-week treatment. (See [section 7.2](#) for the details of hypothesis testing.)

As previously mentioned, the randomization allocation ratio of 1:1:1:1:2 of 10 mg, 25 mg, 50 mg, 25 mg BID of BI 409306, and placebo is used so that 33 % of patients will be randomized to placebo. Since these results in an unequal allocation of treatment to placebo, the sample size required for the active treatment and placebo for various effect size are displayed separately. The sample size calculations in [Table 7.6:1](#) displays the range of effect sizes considered for this trial under these assumptions using a 2-sided alpha of 0.05 with 80 % power. The two-sample t-test method with unequal n's in nQuery Advisor 6.01 was used for the calculation.

Table 7.6: 1 Sample size calculations

Standardized effect size	0.45	0.50	0.55	0.6	0.65
Power	80%	80%	80%	80%	80%
n for each active treatment arm	59	48	40	34	29
n for placebo arm	118	96	80	68	58
Total	354	288	240	204	174

Based on the calculations provided in [Table 7.6:1](#), a sample size of 48 per active treatment arm and 96 for placebo arm was selected as adequate for a phase II proof of concept trial. This sample size would allow us to detect an effect size of 0.5 with 80 % power or an effect size of 0.6 with 92 % power, 2-sided alpha at 0.05.

*Assuming a 10% dropout rate, this sample size would allow us to detect an effect size of 0.53 with 80% power and assuming a 20% dropout rate, this sample size would allow us to detect an effect size of 0.56 with 80% power, 2-sided alpha at 0.05.*

Proprietary confidential information.

© 2017 Boehringer Ingelheim International GmbH or one or more of its affiliated companies. All rights reserved.  
This document may not - in full or in part - be passed on, reproduced, published or otherwise used without prior written permission.

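### Protocol 7.2 tests the quadratic dose response only after a significant straight-line slope, which can block the curve it is meant to find, and the 80% power in 7.6 is for one fixed dose rather than the peak-dose hypothesis named there

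*Protocol*

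**What the plan says.** Protocol 7.2 sets out three steps for the NTB change at week 12. Step 1 compares the pooled active doses with placebo.

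Step 2 writes a model with dose and dose squared. Under the label "Testing for linear dose response curve" it tests H2-0 (β1 = 0 and β2 = 0) against H2-a (β1 ≠ 0, β2 = 0). If H2-0 is rejected in favour of H2-a, "then the following test will be tested for quadratic dose response curve". For Step 3: "Once the dose response curve is determined from Step 2, the dose group with peak response in the selected model will be tested".

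Two statements in the same section limit the stakes: "No multiplicity adjustment will be made; hence all the p-values will be descriptive" and "In addition to the 3 steps above, the confidence intervals of difference in treatment effect against placebo will be presented for efficacy evaluation".

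On the purpose of the dose range, protocol 4.1.3 says: "To study the dose-response relationship, a lower dose (10mg) and a higher dose (50mg) will also be tested".

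Protocol 7.6 states: "The primary efficacy hypothesis will be tested by comparing the dose group of BI 409306 with the peak response in the fitted regression model", and refers to 7.2 for the details. On method it says: "The two-sample t-test method with unequal n's in nQuery Advisor 6.01 was used for the calculation". Its result is 48 per active arm and 96 on placebo for a standardised effect of 0.5 with 80% power.

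SAP 9.3 fits dose and dose squared in one PROC GLM call, scoring 25 mg BID midway between 25 and 50. It does not say which output line is the Step 2 test. SAP 7.4.1 points to protocol 7.3.1 for hypothesis testing, although the steps are in 7.2.

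**The concern.** H2-a fixes β2 at zero, so the gate is a test of the straight-line slope. When a response climbs to a middle dose and falls at the top one, the rise and the fall offset each other and the slope is small even though the curvature is large. The plan would then stop before looking at β2 and report no dose response. If the slope just reaches significance but β2 does not, it would report a straight line with its peak at 50 mg. Step 3 takes its dose from the selected model, so the loss carries forward. The visible text does not say what Step 3 does when H2-0 is not rejected.

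Section 7.6 then attaches 80% power to that peak-dose comparison while computing it for a single dose fixed in advance. A reader would take the 80% as covering the whole Step 2 to Step 3 route, whose success depends on the shape of the curve.

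**Working it through.** **Inputs from the documents.** n = 96 placebo and 48 in each of four active arms (7.6); two-sided 0.05 (7.2); best effect 0.5 SD (7.6); dose scores 0, 10, 25, 37.5, 50, with BID = (25 + 50)/2 (SAP 9.3).

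**Assumptions.** SD 1, complete data, and the peak sought among the active arms. The documents give no curve, so several were tried. The three that turn down (0, 10, 25, 37.5, 50) are:
- A: 0, 0.25, 0.5, 0.5, 0.25
- B: 0, 0.25, 0.5, 0.375, 0.25
- C: 0, 0.32, 0.5, 0.375, 0

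**The plan's own figure.** For a two-sample t-test the non-centrality is δ√(n1·n2/(n1+n2)) = 0.5 × √(48 × 96/144) = 2.83 on 142 df, which gives 80.2%. An effect of 0.6 gives 92.1%. With 10% dropout (43/86) an effect of 0.53 gives 80.4%; with 20% dropout (38/77) 0.56 gives 80.0%. Section 7.6 is reproduced for one fixed dose against placebo.

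**Slope gate.** Mean dose = 48 × (10 + 25 + 37.5 + 50)/288 = 20.42. Sxx = 48 × (10² + 25² + 37.5² + 50²) − 288 × 20.42² = 222,300 − 120,050 = 102,250, so √Sxx = 319.8. The non-centrality is Sxy/√Sxx, where Sxy = Σ n·d·μ − 20.42 × Σ n·μ.
- Linear to 0.5 at 50 mg: 1022.5/319.8 = 3.20, power 89.0%
- A: 750/319.8 = 2.35, power 64.7%
- B: 647.5/319.8 = 2.02, power 52.3%
- C: 257.5/319.8 = 0.81, power 12.6%

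**Joint 2-df test of β1 = β2 = 0.** The non-centrality is Σ n × (fitted quadratic mean − overall mean)². It is 10.2 (linear), 11.9 (A), 9.4 (B) and 12.2 (C), giving 82.0%, 87.7%, 78.4% and 88.6%.

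**Steps 2 and 3 together.** Simulation, 40,000 replicates per shape on group means with pooled error; Step 3 is a pooled-variance contrast standing in for the MMRM. Success means significant in favour of active, and a failed gate stops Step 3.

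| Shape | Slope gate passes | 2-df gate passes | β2 significant but never tested | Quadratic selected, 7.2 / 2-df | Step 3 success, 7.2 / 2-df |
|---|---|---|---|---|---|
| Linear | 89% | 82% | 0.6% | – | 80% / 76–77% |
| A | 64% | 88% | 26% | 45% / 70% | 55% / 76% |
| B | 52% | 78% | 30% | 33% / 60% | 44% / 69% |
| C | 12% | 89% | 81% | 11% / 87% | 11% / 77% |

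Shapes that do not turn down are little affected. Slope and 2-df gates pass in 91% and 87% for Emax with ED50 25 mg, 86% and 92% for a plateau from 10 mg, and 93% and 93% for a plateau from 25 mg. A mild fall, keeping 80% of the peak at 50 mg, gives 85% and 90%. For linear, Emax and plateau shapes the 7.2 route reaches Step 3 success in 80–86%.

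If a failed gate fell back to the straight line, success for A, B, C would be 55%, 46% and 18%, so that reading does not rescue the route.

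With 20% dropout (77 and 38 per arm) the 7.2 route gives 69% for linear and 44%, 35%, 9% for A, B, C; the 2-df gate gives 65% and 65%, 58%, 66%.

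**Flat response.** The slope gate passes in 5.0% and the 2-df gate in 5.1%. Step 3 in favour of active occurs in about 1.5% as written and 1.6% with the 2-df gate.

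**Which output line is read.** In the two-term SAP model, the β1 test adjusted for dose squared is significant in 14% of trials when the truth is linear (straight-line slope 89%) and in 94% under C (straight-line slope 12%).

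**The case against.** **7.6 may mean the fitted quadratic, with no gate.** It speaks of the fitted regression, and only the quadratic is coded in SAP 9.3. Testing the peak of that fit always would give 84%, 78% and 81% for A, B, C, so 80% would roughly hold. But 7.6 sends the reader to 7.2 for the testing, and 7.2 takes the peak from the selected model. Dropping the gate altogether also has a price: about 5.0% of flat-response trials would give a result in favour of active, against 2.5% for one fixed dose.

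**H2-0 is written as the joint null, and the SAP call prints its F test.** True, and this is why the repair is easy. The stated alternative still has β2 = 0 under a heading about a linear curve, so the text as it stands points to the slope.

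**No document predicts a down-turn.** This stands. Protocol 4.1.3 reports CSF exposure rising with dose, which fits a rising or plateau curve at least as well. Shape C is extreme. A and B keep half the benefit at 50 mg and still lose 21 and 25 points at Step 3. A plan that includes a quadratic term and a search for the peak should be able to reach them.

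**Redaction.** SAP text is blacked out near 7.4.1 and 7.5, and MCPMod appears in the abbreviation list without visible use. Further dose-response rules may exist, so the absence of a visible Step 3 fallback is not counted as an error. The gate itself is visible, and the visible text of SAP section 4 lists no change to it.

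**Small consequence.** Largely accepted: p-values are descriptive, and Step 1 (66–98% power over these shapes) and the confidence intervals do not depend on Step 2.

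**Conclusion.** The concern holds in both parts. The slope gate in 7.2 can prevent the curvature test when the response falls at the top dose: under the assumed shapes it costs about 21 to 66 points of Step 3 success compared with a joint gate, and almost nothing when the response is linear, Emax or a plateau. The 80% in 7.6 is correct for one fixed dose against placebo but is not a general power for the peak-dose hypothesis that the section names. N is not wrong.

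The sizes rest on assumed curves, complete data and a pooled-variance stand-in for the MMRM. Importance is minor to moderate: the trial is exploratory, but exploring dose response is one of its stated objectives. It should be fixed.

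**What to change.** 1. **Protocol 7.2, Step 2.** Test β1 = β2 = 0 jointly (2 df, 0.05). If rejected, use the β2 test to choose between the quadratic and the linear curve.
2. **Protocol 7.6.** State that the 80% is for one fixed dose against placebo, and give Step 2 to Step 3 power for two or three named shapes, for example linear, Emax and half of peak at 50 mg.

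Clarifications to make at the same time:

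3. State the Step 3 rule when Step 2 is not rejected. One option is that no curve is selected, Step 3 is not run, and the dose-versus-placebo differences are reported with 95% confidence intervals. With a flat response this gives a Step 3 result in favour of active in 1.6% of trials, against 4.1% if Step 3 always runs on the curve chosen by β2.
4. In SAP 9.3, label the overall model F as the Step 2 test and the dose-squared line as the β2 test. In SAP 7.4.1, cite protocol 7.2 as well as 7.3.1.

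**Cost.** Wording only, since the existing call already prints the 2-df F. If the response is exactly linear, Step 2 power falls from 89% to about 82% and Step 3 success from 80% to 76–77%. For Emax with ED50 25 mg the losses are about 4 and 2 points.
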